6.1.8 Procedures for the Replacement of Patients

The number of included patients will be followed to obtain **C** evaluable patients.

Included patients who withdraw will not be replaced by another patient. The patient number and associated inclusion number of the withdrawn patient must not be reassigned to a different patient.

6.1.9 Investigation Sites

Patients will be enrolled in approximately 6 investigational sites in EU.

The Sponsor will maintain an updated list of PIs and investigation sites, separately from this CIP, throughout the duration of the clinical investigation. The definitive list will be provided with the CIR.

6.1.10 Definition of Completion of the Clinical Investigation

The clinical investigation completion is defined with the last visit of the last patient.

In the case of early termination of the clinical investigation (see Section 16.2), the date of the early termination shall be deemed to be the date of the clinical investigation completion.

6.2 IMD(s) AND COMPARATOR(S)

6.2.1 Description of the Exposure to the IMD

IMD will be administered by the patient every day for 36 + 3 days, one drop in each eye 3 to 6 times daily into the lower conjunctival sac of each eye.

No IMD instillation must be performed at least 2 hours before Visit#2 and 3. However, the first instillation can be done any time after the patient has completed the inclusion visit.

There will be only 1 treatment group, all patients will instil T2769.

A detailed description of T2769 is available in Section 2.

6.2.2 List of any Other Medical Device or Medication to be Used during the Clinical Investigation

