1.4 OVERALL SYNOPSIS OF THE CLINICAL INVESTIGATION

Title	Performance and safety assessment of T2769 in contact lens wearers with dry eye symptoms.
Sponsor	Laboratoires THÉA
Sponsor Investigation No.	LT2769-003
Investigation Centre(s)	This investigation is planned to be carried out at approximately 6 sites in European Union (EU).
Planned Schedule	Planned initiation: August 2023 Planned last patient last visit: January 2024
Primary Investigation Objective	To assess the performance of T2769 in contact lens wearers with dry eye symptoms in terms of change from baseline (Day 1) to Day 36 (Final visit) in Contact Lens Dry Eye Questionnaire-8 (CLDEQ-8) total score.
Secondary Investigation Objective(s)	To assess the performance and safety of T2769 in contact lens wearers with dry eye symptoms.
Sample Size	cc1 evaluable patients
Investigation Design	A prospective, single-arm, multicenter, 5-week investigation. Three visits: Visit #1: Day 1 Inclusion visit (D1) Visit #2: Day 15 (± 1 day) (D15) Visit #3: Day 36 (+3 days) Final visit (D36) All visits must take place in the afternoon.
Investigation Duration	
 ▪ Treatment period: 36 +3 days 
Total investigation duration: maximum of 39 days

Investigational Medical Device (IMD)	
Formulation: T2769: sodium hyaluronate 0.15%, Trehalose 3%, Naaga 2.45% in a 12.5 mL ABAK® multi-dose bottle.
 
Route of administration: Topical, by ocular route
 
Dose regimen: 1 drop in each eye, from 3 to 6 times daily, at any time but only when patients are wearing their contact lenses.

Inclusion Criteria	
 1.1. Informed consent signed and dated (obtained prior to initiating any procedures). 1.2. Patient aged ≥ 18 years old. 1.3. Well fitted contact lenses (CL) according to the investigator judgement. 1.4. Daily wearer of any type of CL for a minimum of 5 days/week for 6 hours/day over at least the last month and is willing to continue to do so during the study. 1.5. Patient with an Ocular Surface Disease Index (OSDI) score ≥ 18. 1.6. CLDEQ-8 score ≥ 12. 
CCI

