6 DESIGN OF THE CLINICAL INVESTIGATION

6.1 GENERAL

6.1.1 Justification of the clinical investigation design

Methodology: a prospective, single-arm, multicenter, 5-week investigation.

- Multicenter

Multicenter (and multi-investigator) design will provide the possibility of recruiting the patients from a wider population and of using the device in a broader range of clinical settings, thus presenting an experimental situation that is more typical of future use. In this case, the involvement of a number of investigators also gives the potential for a wider range of clinical judgment concerning the value of the therapeutic intervention. In addition, it is also a practical mean of accruing sufficient patients to satisfy the investigation objective within a reasonable timeframe.

- Single arm / open label design

This is a confirmatory clinical investigation to collect data on contact lens wearers with dry eye symptoms.

- Choice of the investigation population

The study population will consist of patients wearing well fitted contact lenses for a minimum of 5 days/week for 6 hours/day over at least the last month before inclusion visit and experiencing some dry eye symptoms as defined in inclusion criteria.

- Scheme of administration

The dose regimen recommended is 3 to 6 times daily. Patients can instil IMD at any time during the day, but only when wearing their contact lenses.

- Choice of the treatment period

A 5-week treatment period may allow to evaluate the therapeutic effect and to observe any potential safety issues.

A period of 1 month is usually the minimum time required to demonstrate the therapeutic effect of a product.

- Choice of primary endpoint and secondary endpoints

The primary and secondary endpoints of this clinical study have been taken into consideration based on the clinical literature review (Chalmers et al. 2016; Chalmers et al. 2012; Pucker et al. 2020; Fernández-Jimenez, Diz-Arias et Peral 2022). Consequently, these endpoints are clinically relevant, clearly defined and assessed at specified time points to provide clinical evidence on the performance and tolerance of T2769 in its intended use (i.e., improvement of the ocular signs and symptoms in DED patients).

- Symptoms assessment

Ocular symptoms as well as AEs will be assessed at all investigation visits.

The investigation flow chart is described in Table 2.

6.1.2 Description of the Measures to be Taken to Minimize or Avoid Bias**6.1.2.1 Randomisation**

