6.3 SUBJECTS/PATIENTS

6.3.1 Inclusion Criteria

Patient fulfilling all the following criteria will be eligible:

- 1.1. Informed consent signed and dated (obtained prior to initiating any procedures).
- 1.2. Patient aged ≥ 18 years old.
- 1.3. Well fitted contact lenses (CL) according to the investigator judgement.
- 1.4. Daily wearer of any type of CL for a minimum of 5 days/week for 6 hours/day over at least the last month and is willing to continue to do so during the study.
- 1.5. Patient with an Ocular Surface Disease Index (OSDI) score ≥ 18 .
- 1.6. CLDEQ-8 score ≥ 12 .

CCI

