4.3 Study Treatments and Procedures

Study Treatment

There is one group of investigational medical device (IMD):

- T2769: Sodium hyaluronate (0.15%), Trehalose (3%), N-Acetyl Aspartyl Glutamic Acid Sodium salt (Naaga, 2.45%), sodium hydroxide (for pH adjustment) and water for injections in a 12.5 mL ABAK® multi-dose bottle.

IMD is administered by the patient every day for 36 + 3 days, one drop in each eye 3 to 6 times daily (at any time during the day, but only when wearing their contact lenses), into the lower conjunctival sac of each eye.

No IMD instillation should be performed at least 2 hours before Visit #2 and #3. However, the first instillation could be done any time after the patient has completed the inclusion visit.

There is only 1 treatment group, all patients instil T2769.

Procedures

Schedule of assessments and procedures is presented in Section 1.4 of the protocol.

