5.2 Data Derivations

Baseline and Change from baseline

Baseline and change from baseline will be calculated for all assessments as follows:

- Baseline value is defined as the assessment at inclusion visit before the first IMD instillation.
Missing value at inclusion visit will not be replaced.

- Change from baseline will be calculated as the difference between the assessment value and the baseline value.
- Change from baseline in classes will be defined as follows in three classes compared to 0:
 - Improvement (Decrease of score from baseline): Change from baseline < 0,
 - Stable: Change from baseline = 0,
 - Worsening (Increase of score from baseline): Change from baseline > 0.

Study Day

Study day will be calculated as (assessment date - date of first IMD) for pre-baseline assessments and [(assessment date - date of first IMD) + 1] for post-baseline assessments, e.g., there will be no study day 0 and study day 1 will correspond to the first IMD.

Age

Age (years) will be calculated in classes as: < 65, \geq 65 and < 85, \geq 85 years.

Time since DED diagnosis

Time since DED diagnosis (months) will be calculated as (Date of inclusion visit - Date of diagnosis) / 365.25 x 12.

If the day is missing and month is present the 15 of the month will be used. If year is present and day and month are missing, the time since DED diagnosis will be calculated as (Year of inclusion visit - Year of diagnosis) x 12.

Duration of exposure

Duration of exposure (days) will be calculated as (Date of last instillation - Date of first instillation) + 1.

If the day or the month is missing for one of the dates, the duration of exposure will be missing.

Number of days with instillation of T2769

Number of days with instillation will be calculated for both eyes together as follows:

- From D1 to D15: (Date of Visit #2 - Date of inclusion Visit + 1) - (Number of days without instillation of IMD recorded in the eCRF at Visit #2).
- From D15 to D36: (Date of Visit #3 - (Date of Visit #2 + 1) + 1) - (Number of days without instillation of IMD recorded in the eCRF at Visit #3).
- From D1 to D36: Sum of number of days with instillation from D1 and D15 and from D15 and D36.

CCI

Sponsor: Laboratoires Théa

Protocol: LT2769-003

Statistical Analysis Plan: V1.0 / 26-OCT-2023

CLDEQ-8 total Score

CCI

OSDI

CCI

Total score of ocular symptoms throughout the day

CCI

Mean contact lens wearing time as mean number of days/week

CCI

TBUT

CCI

Total ocular surface staining grade

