7.7 Treatment Exposure and Compliance

The following data on the use of the IMD will be summarized using descriptive statistics overall using the FAS and PPS:

- Treated eye (Right eye / Left eye/ Both eyes),
- Duration of exposure (days),
- Mean daily dose regimen (less than 3 / 3 instillations/day / 4 instillations/day / 5 instillations/day / 6 instillations/day and more than 6) at D15 and D36,
- Total number of days with study treatment (between D1 and D15, between D16 and D36 and between D1 and D36) for the studied eye and the contralateral eye separately.

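### Dosing every day and dosing only during lens wear cannot both be followed by an eligible 5-day-a-week wearer, and the visible SAP does not say how lens-free days count

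*Protocol*

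**What the plan says.** Two dosing rules appear in the operative text.

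- **Every day.** Protocol 6.2.1: "IMD will be administered by the patient every day for 36 + 3 days", at 3 to 6 instillations daily, with no reference to lens wear.
- **Only during lens wear.** The synopsis (Protocol 1.4) allows drops "at any time but only when patients are wearing their contact lenses". Protocol 6.1.1 says the same: "Patients can instil IMD at any time during the day, but only when wearing their contact lenses".
- **Both together.** SAP 4.3 opens with "IMD is administered by the patient every day for 36 + 3 days" and, in the same sentence, adds the condition "at any time during the day, but only when wearing their contact lenses".

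Criterion 1.4 (Protocol 6.3.1) sets the minimum lens wear: "Daily wearer of any type of CL for a minimum of 5 days/week for 6 hours/day". Patients must also be willing to keep this up during the study, so up to two lens-free days a week are compatible with eligibility.

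On the analysis side, SAP 5.2 derives days with instillation as calendar days between visits minus an eCRF item, "Number of days without instillation of IMD recorded in the eCRF at Visit #2", with a matching item at Visit 3. SAP 7.7 tabulates the dose level in classes: "Mean daily dose regimen (less than 3 / 3 instillations/day / 4 instillations/day" and upward. Neither section visibly mentions lens-free days or gives the denominator of that mean. The list of potential deviations is held in a separate document (SAP 7.3).

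**The concern.** The two rules coincide only for someone who wears lenses 7 days a week. For anyone else, a lens-free day is either a day on which drops are due or a day on which they are not allowed, depending on which section a site reads. The instructions for use reproduced at the end of the protocol, a version of which patients receive, give the 3 to 6 times daily dosage without the lens condition. Different instruction across the roughly 6 sites is therefore a realistic risk.

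Two things are at stake. First, the exposure received may depend on which section was followed, and no planned table would show it. Second, the meaning of a missed dose is undefined. Protocol 6.4.1.3.6 assesses compliance partly by asking about missed instillations, and whether a lens-free day is one depends on the rule. Without a single rule, a dosing deviation cannot be defined in the same way at every site. The per-protocol repeat, which is the only sensitivity analysis planned for the primary endpoint, rests on that definition.

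**Working it through.** **Inputs**

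- Treatment period: 36 days plus up to 3 (Protocol 6.3.7).
- Minimum lens wear: 5 days a week (criterion 1.4).
- Visits at D1, D15 and D36, with lenses worn to each (Protocol 6.1.6).
- Days with instillation: calendar days minus recorded days without instillation (SAP 5.2).
- Assumption: a fixed weekly pattern of exactly two lens-free days, with the first instillation on D1.

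**Stated figure.** 36 + 3 = 39 days, which matches the maximum duration in Protocol 6.3.7.

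**Lens-free days to D36.** D15 is 14 days after D1 and D36 is 35 days after D1, so all three visits fall on the same weekday, which must be a lens day. D1 to D36 is five full weeks plus one more lens day:

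- lens-free days = 5 × 2 = 10, or 10/36 = 27.8%;
- lens days = 36 − 10 = 26, or 72.2%.

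**SAP 5.2 formula for a patient who doses only on lens days**

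- D1 to D15: 15 calendar days − 4 = 11.
- D16 to D36: 21 calendar days − 6 = 15.
- Total: 11 + 15 = 26. A patient who doses every day has 36.

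The count is arithmetically right in both cases. However, 26 could equally describe a patient who was told to dose daily and missed 10 days.

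**Sensitivity.** If the final visit falls on D39, the lens days number 27 to 29 of 39 (69.2% to 74.4%), depending on which weekdays are lens-free. At 6 lens days a week there are 31 of 36.

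**Mean daily dose, by denominator, over 36 days at 5 lens days a week**

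| Instillations per lens day | Per calendar day (k × 26/36) | Per instillation day |
|---|---|---|
| 3 | 2.17 | 3 |
| 4 | 2.89 | 4 |
| 5 | 3.61 | 5 |
| 6 | 4.33 | 6 |

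Only with a calendar-day denominator do patients using 3 or 4 a day on lens days drop into the class below 3. At 6 lens days a week the calendar-day means are 3 × 31/36 = 2.58 and 4 × 31/36 = 3.44, so only the first drops. The visible text does not say which denominator applies.

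**The case against.** A reader might infer that the exposure tables will show adherent patients as under-dosed, and that some will be removed from the per-protocol set for obeying one of the protocol's own rules. The documents do not support going that far, for these reasons:

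- Duration of exposure in SAP 5.2 runs from first to last instillation, so lens-free days in between leave it unchanged. The count of days with instillation is a correct count. SAP 7.7 lists no compliance percentage and no adherent or non-adherent class.
- The dose classes are whole numbers reported at D15 and D36, which also fits a category recorded at each visit. If so, or if the average is over instillation days, nothing moves. The derivation may sit in the blacked-out part of SAP 5.2.
- No compliance threshold is visible and the deviation list was not supplied. Per-protocol exclusion requires a major violation likely to affect the primary outcome seriously, and it is decided at a review meeting before database lock, where lens-free days could be considered.
- Protocol 7.16 plans training and standardised procedures, so differing instruction is a risk, not a certainty.
- The 5-day case is the eligibility minimum. The documents do not say how many patients wear lenses on fewer than 7 days a week.

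All of this stands as a limit on the consequences. None of it removes the conflict. Reading the daily rule as covering lens days only would be charitable, but Protocol 6.2.1 does not say so. Even on that reading, the visible SAP text does not say how lens-free days enter the count or the mean.

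**Conclusion.** The contradiction is established: Protocol 6.2.1 conflicts with the synopsis and 6.1.1, SAP 4.3 carries both rules, and criterion 1.4 admits patients who cannot satisfy them together. At 5 lens days a week the gap is 10 of 36 days, or 26 against 36 instillation days, given a fixed weekly pattern and visits on lens days.

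What follows for the analysis is narrower. Exposure may vary with the rule a site applied, and the visible day count cannot tell a permitted lens-free day from a missed one. Movement into the lowest dose class is conditional on a calendar-day denominator that the visible text does not show. Wrong per-protocol exclusions are possible but not demonstrated. The primary result, an observed-case paired comparison on the FAS, does not depend on how adherence is classified. Which dosing rule should stand is not judged here.

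**What to change.** 1. The sponsor should reconcile the synopsis, Protocol 6.1.1, Protocol 6.2.1 and SAP 4.3 so that a single rule covers lens-free days.
2. SAP 5.2 should state whether a lens-free day counts as a day without instillation, following that rule.
3. SAP 5.2 and 7.7 should define the mean daily dose using as denominator the days on which the retained rule calls for drops.
4. The separate deviation list should define a dosing deviation on the same basis, before the data review meeting.

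The cost is a wording amendment and changes to the exposure derivations. The paper diary already collects daily instillations and daily hours of lens wear, so patients need record nothing new. The visible SAP, however, draws on a per-visit total of days without instillation from the eCRF. It should therefore be confirmed that day-level diary data are entered. If they are not, matching lens-free days to instillation days would need extra data entry from the diaries.

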6.2.2.1 Run-in Treatment/Wash-out Treatment

Not Applicable.

6.2.2.2 Auxiliary Products

An auxiliary product is defined as a product used for the needs of a clinical investigation as described in the CIP, but not as an IMD.

Fluorescein Faure 0.5% unidoses: one drop will be instilled in the upper bulbar conjunctiva of each eye by the investigator at visits 1, 2 and 3 to perform the slit lamp examination: TBUT and corneal/conjunctival staining with Oxford 0-15 grading scheme. This staining is assessed with a yellow filter.

Schirmer-Plus: while the patient looks upwards, the lower lid will be drawn gently downwards and temporally. The rounded bent end of a sterile Schirmer test strip will be hooked in the lower conjunctival sac over the temporal one-third of the lower eyelid margin. After five minutes, the

moistened paper is removed and the length of the tear absorption on the strip will be measured (in millimeters).

Pregnancy test: each childbearing potential woman will perform a urine pregnancy test at Visit#1 and Visit#3.

6.2.3 Number of IMD to be Used, together with a Justification

During the clinical investigation, each patient will receive the IMD (2 vials of T2769) to cover active treatment period. One 12.5 mL ABAK® multi-dose bottle can deliver up to about 375 drops which is enough to cover 39 days treatment period taking into consideration a maximal dose regimen of 1 drop in each eye 6 times daily.

6.3 SUBJECTS/PATIENTS

6.3.1 Inclusion Criteria

Patient fulfilling all the following criteria will be eligible:

- 1.1. Informed consent signed and dated (obtained prior to initiating any procedures).
- 1.2. Patient aged ≥ 18 years old.
- 1.3. Well fitted contact lenses (CL) according to the investigator judgement.
- 1.4. Daily wearer of any type of CL for a minimum of 5 days/week for 6 hours/day over at least the last month and is willing to continue to do so during the study.
- 1.5. Patient with an Ocular Surface Disease Index (OSDI) score ≥ 18 .
- 1.6. CLDEQ-8 score ≥ 12 .

CCI

6.3.2 Exclusion Criteria

[figure not shown]
Patient will NOT be eligible if ONE OR MORE of the following criteria is met:

Ophthalmic Exclusion Criteria in AT LEAST ONE EYE [2.1]

- 2.1.1. Far Best-Corrected Visual Acuity (BCVA) $\geq +0.7$ LogMar (e.g., ≤ 0.2 in decimal value or $\leq 20/100$ Snellen equivalent or ≤ 50 ETDRS letters).
- 2.1.2. Severe blepharitis according to the judgment of the investigator.
- 2.1.3. Confirmed diagnosis of severe Meibomian gland dysfunction.
- 2.1.4. Presence of palpebral or nasolacrimal disorders.
- 2.1.5. Dry eye associated with at least one of the following diseases/symptoms:
 - Ocular rosacea,
 - Pterygium,
 - Eyelid malposition,
 - Corneal dystrophy,
 - Ocular neoplasia,

- Filamentous keratitis,
- Corneal neovascularisation,
- Orbital radiotherapy,
- Cataract,
- Retinal disease.

CCI

6.3.3 Criteria and Procedures for Treatment/Investigation Withdrawal or Discontinuation

There are no pre-defined criteria for temporary or permanent treatment discontinuation apart from those listed below.

The patient may voluntarily withdraw from the clinical investigation at any time without penalty and for any reason without prejudice to his/her future medical care (Declaration of Helsinki).

The patient must be withdrawn from the clinical investigation if, in the opinion of the investigator, there is any situation or condition which puts the patient at significant risk, especially in case of:

- Any safety reason(s)/AEs necessitating discontinuation from the investigation,
- Any abnormality with IMD,
- Lack of performance: if the patient or the investigator does not feel that the IMD has sufficiently controlled the pathology/has adequately relieved his/her symptoms,
- Patient compliance,
- Patient's request,
- Any exceptional circumstance (e.g., COVID-19 pandemic),
- Other reasons.

If a patient prematurely stops the IMD or should/wants to prematurely withdraw from the clinical investigation for any reason, the investigator (or delegated assessor) must make every effort to perform all the evaluations described for the final visit (Visit#3) as soon as possible.

The investigator (or delegated assessor if physician) will prescribe the best appropriate treatment to the patient.

In all cases, the reason(s) for withdrawal, must be recorded on the patient files (source documentation) and the primary reason, must be recorded on the e-CRF.

The patient discontinued for AE(s) will be followed-up after discontinuation until the event is resolved or considered medically stable by the investigator.

If a patient is lost-to-follow-up, the investigator must do his/her best to contact the patient initially by phone, then by letter, and finally by certified mail. If no response is obtained from the patient, the investigator is encouraged to contact one of the patient's relatives or his/her general practitioner. The evidence of these contacts must be recorded in the patient files.

Screen failures are defined as patient who consent to participate in the clinical investigation and undergo visit#1 but are not subsequently included in the investigation.

If a patient is screen-failed, all reasons of screen-failure must be documented in the Source document. The screen-failed patient may be rescreened one time.

Adaptive follow-up in the case of an **exceptional circumstance (e.g. COVID-19 pandemic)** is described in section 6.1.6.6.

